## Statistical Analysis Plan (SAP)

A standard randomized controlled design will be adopted in this study, and we will randomly assign 40 patients to either active tDCS or sham tDCS (20 per group). Our primary analysis will compare clinical pain changes from baseline to the final intervention session between the active tDCS and sham tDCS groups. We plan to conduct 2 hypothesis tests for the main outcomes (MOBID-2 and fNIRS at Day 5) at a family-wise significance level of  $\alpha = 0.025$  after Bonferroni correction. With the sample size 20 per group, we will be able to detect the expected effect size of 1.0 with 80% power at a significance level of 0.025.

All data will be analyzed using the intention-to-treat approach. All demographic and clinical variables will be summarized using descriptive statistics, such as mean  $\pm$  standard deviation or median (interquartile range) as appropriate for continuous variables and frequency and percentage for categorical variables. The distribution of all variables will be examined to check the validity of distribution assumptions before any analysis, using measures of central tendency and a visual inspection of histograms and quantile-quantile plots. If the assumption of normality is not met, nonparametric approaches will be employed. SAS 9.4 (SAS Institute, Cary, NC) will be used to perform the proposed statistical analyses.

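### For the SAP's two main tests, Holm would keep the same overall 5% error as Bonferroni and improve the chance of supporting both hypotheses, provided the overall level is stated as 0.05

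*SAP*

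**What the plan says.** The first paragraph of the SAP sets up a family of two tests: "We plan to conduct 2 hypothesis tests for the main outcomes (MOBID-2 and fNIRS at Day 5"). It gives their level as 0.025, obtained "after Bonferroni correction". It labels that figure family-wise, but the power sentence that follows, for groups of 20, applies it to one test: "we will be able to detect the expected effect size of 1.0 with 80% power at a significance level of 0.025". Since 0.05/2 = 0.025, the natural reading is 0.025 per test and 0.05 overall.

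The SAP names no step-down, hierarchical or gatekeeping rule. It gives no power for supporting both hypotheses, no correlation between the outcomes, and no sidedness. The protocol contains no multiplicity rule. Protocol Section 6.0 makes MOBID-2 the primary outcome, and its Table 1 lists fNIRS as secondary. Section 10.0 caps enrolment at 40, and Section 12.0 reports that data for 20 participants were already collected at the previous institution.

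**The concern.** Under single-step Bonferroni each p-value must reach 0.025 whatever the other test shows. If fNIRS passes clearly and MOBID-2 has p = 0.04, MOBID-2 is declared negative. Holm would declare it positive at the same overall error rate: once one hypothesis has been rejected at half alpha, only one remains and it can be tested at full alpha.

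This matters because the sample cannot grow and the planned power only just reaches its target. Protocol Section 2.0 makes clinical pain and cortical response separate aims, so a result on each is wanted.

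**Working it through.** **Inputs from the SAP.** Two tests, 20 per group, standardised effect 1.0, level 0.025 in the power sentence, stated power 80%.

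**Assumptions, because the documents are silent.** Two-sided two-sample t-tests; effect 1.0 on both outcomes (the SAP gives one value and ties it to neither); no dropout; independent outcomes in the base case, with correlations up to 0.8 shown.

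**Step 1: reproduce the plan's figure.** Noncentral t with 38 degrees of freedom and noncentrality 1.0 × √(20/2) = √10:
- at 0.025 two-sided, power = 0.7926, which matches the stated 80%;
- at 0.05 two-sided, power = 0.8690;
- at 0.025 one-sided, power = 0.869, which does not match, so two-sided is used.

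The normal approximation gives 82.1% at 0.025, and a requirement of 20 per group for 80%.

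**Step 2: both hypotheses supported, independent outcomes.**
- Bonferroni needs both p ≤ 0.025: 0.7926² = 0.628.
- Holm needs both p ≤ 0.05 and at least one p ≤ 0.025: 0.8690² − (0.8690 − 0.7926)² = 0.7552 − 0.0058 = 0.749.

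The gain is 74.9 − 62.8 = 12.1 points.

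**Step 3: power for one test under Holm.** 0.7926 + (0.8690 − 0.7926) × 0.7926 = 0.853, against 0.793 under Bonferroni.

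**Step 4: at least one supported.** 1 − (1 − 0.7926)² = 0.957 under either method, because the first Holm step is the Bonferroni test.

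**Step 5: correlation** (200,000 simulated trials per setting, effect 1.0 on both).

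| Correlation | Both, Bonferroni | Both, Holm | MOBID-2 power, Holm | At least one, either method |
|---|---|---|---|---|
| 0.3 | 65.5% | 76.3% | 84.8% | 93.2% |
| 0.5 | 67.5% | 77.6% | 84.3% | 91.1% |
| 0.8 | 71.9% | 80.1% | 83.4% | 86.8% |

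**Step 6: weaker fNIRS effect** (independent outcomes, MOBID-2 effect 1.0, MOBID-2 power 79.3% under Bonferroni throughout).

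| fNIRS effect | Both, Bonferroni | Both, Holm | MOBID-2 power, Holm |
|---|---|---|---|
| 0.8 | 46.1% | 59.4% | 83.7% |
| 0.5 | 18.9% | 28.6% | 81.1% |
| 0 | – | – | 79.5% |

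With 18 evaluable per group and effect 1.0 on both, the chance of both goes from 54.9% to 68.1%.

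**Step 7: error control.** Simulated family-wise error under Holm is 4.9% (correlation 0) and 4.7% (correlation 0.5) with both nulls true, and 4.5% and 4.3% with only fNIRS null. It stays below 5%, as theory requires.

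**Step 8: why the level must be restated.** If only the method name were changed and 0.025 stayed as the family-wise level, the thresholds would become 0.0125 and then 0.025. Power at 0.0125 is 0.7034, so:
- per test: 0.7034 + 0.7034 × (0.7926 − 0.7034) = 0.766, below 0.793;
- both: 0.7926² − 0.0892² = 0.620, below 0.628;
- at least one: 1 − (1 − 0.7034)² = 0.912, below 0.957.

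All three would be worse than testing each outcome at 0.025.

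**The case against.** **Bonferroni is pre-specified and valid.** This stands. A reader might infer that the SAP fails to control its error rate. It does not fail; what is lost is efficiency.

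**The headline gain is not trial success.** A reader might infer that Holm raises the chance of a successful trial by 12 points. No document defines success as both tests passing, and the chance of at least one success does not move. The 12 points also rest on independence and an effect of 1.0 on fNIRS, neither of which the SAP states. Among the correlations checked, independence gives the largest gain.

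**The primary outcome gains only through fNIRS.** This stands. The six-point gain for MOBID-2 needs an fNIRS effect as large as 1.0.

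**The MOBID-2 threshold would depend on a loosely defined test.** Protocol Section 6.0 describes multichannel recording over two cortical regions on both sides, and neither document names a single fNIRS summary. Under Bonferroni the MOBID-2 threshold is insulated from that. This is a fair condition on the change, although Holm never tests MOBID-2 above 0.05.

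**Intervals match Bonferroni more simply.** This stands. Wherever Holm adds a rejection, p lies between 0.025 and 0.05 and the 97.5% interval includes zero.

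**fNIRS may not belong in the family.** If it is secondary, as Table 1 says, Holm is not the natural remedy: MOBID-2 tested first at 0.05 would have 86.9% power. This limits the point but does not defeat it while the SAP keeps two main tests.

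**Half the data are in.** A change of decision rule now has a credibility cost, which depends on its being made blind.

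**Conclusion.** The point holds as a worthwhile improvement, not as the correction of an error. While the SAP keeps two main tests at an overall 0.05, Holm loses no rejection that Bonferroni would make and adds some, with the same family-wise error and no extra patients. That ordering needs no assumption about correlation or effect size.

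The size does need assumptions. With an effect of 1.0 on both outcomes and 20 evaluable per group, the gain in supporting both is about 8 to 12 points for correlations from 0.8 down to 0. For MOBID-2 alone it ranges from about 6 points (fNIRS effect 1.0, independent outcomes) down to 0.2 (no fNIRS effect). All of this depends on reading 0.025 as the per-test level, which the power sentence supports and the family-wise label does not.

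**What to change.** In the SAP sentence that sets the level for the two tests, replace both the stated family-wise level of 0.025 and the words "after Bonferroni correction" with:

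> at an overall two-sided family-wise level of 0.05 using the Holm procedure: the smaller p-value is compared with 0.025 and, if it passes, the larger with 0.05.

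Keep 0.025 in the power sentence as the conservative per-test planning level. Add that the Holm-adjusted p-values decide and that the confidence intervals are descriptive. Name the single fNIRS summary and test that enter the procedure.

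Before adopting this, reconcile the status of fNIRS between the SAP and Table 1 of the protocol. If fNIRS leaves the family, this change falls away.

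Make the change in a dated amendment before any unblinded comparison, because 20 participants' data are already collected. The cost is a few lines of SAP text and the loss of simple intervals that match the decision in every case. No patient, visit or measurement changes.

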#### **5.0 Study Intervention/Investigational Agent**

tDCS with a constant current intensity of 2 mA will be applied for 20 minutes per session daily for 5 days via the Soterix 1x1 tDCS mini-CT Stimulator device (Soterix Medical Inc., NY; 6.5 inches long, 3 inches wide, 0.7 inches thick) with headgear and 5x7 cm saline-soaked surface sponge electrodes. The FDA has ruled that the aforementioned tDCS stimulator is a “non-significant risk” device, a requirement for Investigational Device Exceptions. The sponge electrodes snap into the custom headgear, which is secured to the participant’s head for simple and fail-safe electrode preparation. This single-position headgear with clearly labeled sponge markers eliminates room for user error and helps conserve the placement of the montage. Participants can only administer a stimulation session via the Soterix 1x1 tDCS mini-CT Stimulator device after being provided a single-use unlock code by the research staff once proper contact quality is achieved (only the on/off button will be adjustable by the study participants; they will not be able to adjust the device settings). After the participant enters the unlock code, the screen on the device will show a timer that counts down the minutes until the end of the session. At 20 minutes, the device will turn off automatically, and study staff will instruct the participant to remove the headset and discard the sponges and to safely store all materials for the next session. For sham stimulation, the electrodes will be placed in the same positions as for active stimulation, but the stimulator will only deliver 2 mA current for 30 seconds. This sham stimulation method has been shown to be reliable and indistinguishable from active treatment.

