randomized, sham-controlled, parallel group (1:1 for two groups) pilot clinical trial. The central hypothesis is that home-based, remotely supervised tDCS will decrease pain. This hypothesis will be tested by pursuing the following specific aims: evaluate the preliminary effects of home-based M1-SO applied tDCS on clinical pain in persons with early-stage ADRD (specific aim 1); evaluate the preliminary effects of home-based M1-SO applied tDCS on pain related cortical response in persons with early-stage ADRD (specific aim 2); and evaluate the feasibility and acceptability of home based M1-SO-applied tDCS for pain management in persons with early stage ADRD (specific aim 3). We will also obtain data, as an exploratory aim, to investigate whether tDCS reduces behavioral and psychological symptoms of dementia. The proposed study will directly investigate the effects of home-based, remotely supervised tDCS in 40 persons with ADRD using an experimenter- and participant-blinded, randomized, sham-controlled, parallel group (1:1 for two groups) pilot clinical trial. Caregivers will set up and administer home-based tDCS for persons with ADRD and must be present at each home-based session, and participants will be remotely supervised by trained research staff at each stimulation to ensure the use of proper technique. Primary outcome (clinical pain assessed by the MOBID-2) will be performed by the caregivers. Caregivers will be trained at the in-person baseline visit to use tDCS devices and to perform outcome measures. tDCS session will be not performed if the caregiver is not available, and it needs to be the same caregiver throughout the trial. The proposed research is significant because it is expected to provide valuable insight into an exciting new modality of nonpharmacological pain management that is easy, safe, and noninvasive with minimal side effects.

Participants will do remotely-supervised tDCS at their home or private room for 5 days under real time supervision by the research staff. Data will be collected by study staff across several points using equipment and resources available at [name] (PI's) laboratory at Florida State University (see Table below). The primary endpoint will be clinical pain (MOBID-2) collected after the final intervention session. Participants will visit Florida State University two times, and each visit will take approximately 2 hours.

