## **14.0 Withdrawal of Subjects**

Participation in this study is completely voluntary. All participants will be informed of the nature of the procedures and associated risks. Also, participants will be informed that they can withdraw from the study at any time by calling study team at [contact] and that this will have no adverse impact on the study or on their own future medical treatment.

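### The SAP names no model for the primary MOBID-2 comparison and no rule for a missing session-5 score; a baseline-adjusted repeated-measures model on data already scheduled would be better than a plain change-score comparison

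*SAP*

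**What the plan says.** The SAP has two paragraphs. On the primary analysis it says: "Our primary analysis will compare clinical pain changes from baseline to the final intervention session between the active tDCS and sham tDCS groups". It then says: "We plan to conduct 2 hypothesis tests for the main outcomes (MOBID-2 and fNIRS at Day 5"), each at 0.025. On precision it says: "With the sample size 20 per group, we will be able to detect the expected effect size of 1.0 with 80% power". On the analysed population it says only: "All data will be analyzed using the intention-to-treat approach". If normality fails, unspecified nonparametric methods are to be used.

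The SAP names no t-test, ANCOVA or mixed model, and gives no imputation or likelihood method, no definition of the analysed set and no sensitivity analysis. Protocol section 10.0 says that medications which may affect response will enter the statistical models as covariates, but does not identify those models.

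Table 1 in Protocol section 6.0 schedules MOBID-2 at baseline, at each of sessions 1 to 5 and at three phone follow-ups. It schedules fNIRS at baseline and session 5 only.

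Two further protocol rules bear on whether a session-5 score is obtained. In section 6.0, "tDCS session will be not performed if the caregiver is not available, and it needs to be the same caregiver throughout the trial", and "Primary outcome (clinical pain assessed by the MOBID-2) will be performed by the caregivers". In section 14.0, participants are told that "they can withdraw from the study at any time".

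**The concern.** Intention to treat settles which arm a participant is counted in. It does not settle how someone with no score at the endpoint contributes. The most literal reading of the SAP sentence is a two-group comparison of change scores, and under that reading a participant without a session-5 score has no change score and leaves the comparison.

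Such cases are foreseeable from the trial's own rules. One fixed caregiver must attend every session and also scores the outcome, and withdrawal is open throughout. A missed session need not mean a missing score, since MOBID-2 is also scheduled by phone after treatment ends.

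Three things are at stake. The handling of missing scores, and the choice among change score, ANCOVA and a rank test, could be made after the data are seen. The contrast could be biased if loss relates to pain. And information that the trial collects anyway, namely baseline as a covariate and four intermediate scores, would go unused.

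**Working it through.** **Inputs.** 20 per arm, effect size 1.0, power 80%, level 0.025 (SAP, first paragraph). Maximum enrolment 40 (Protocol 10.0). Assumed, because not stated: the test is two-sided, and 1.0 is in SD units of the change score. No loss rate and no baseline to session-5 correlation are given.

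**1. The SAP's own figure.** For a two-sample comparison with d = 1.0, the noncentrality is d × √(n₁n₂/(n₁+n₂)). At 20/20 this is √10 = 3.162.
- t-test: 38 df, critical value 2.334, power 79.3%.
- Normal approximation: Φ(3.162 − 2.241) = 82.1%. The matching sample-size formula, 2 × (2.241 + 0.842)² = 19.01, rounds up to 20 per arm.

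Both are consistent with the stated 80% at 20 per arm. The SAP does not say which was used.

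**2. Unadjusted comparison with some scores missing.** The losses are illustrative.

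| Scored per arm | t-test power | Normal power | Effect detectable at 80% (t-test) |
|---|---|---|---|
| 20/20 | 79.3% | 82.1% | 1.01 |
| 20/19 | 78.0% | 81.1% | 1.02 |
| 19/19 | 76.8% | 79.98% | 1.04 |
| 18/18 | 74.1% | 77.6% | 1.07 |

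One lost score costs about 1 point. Two cost about 2 to 2.5 points, and four about 4.5 to 5.

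**3. What baseline adjustment changes.** With equal SDs σ at baseline and session 5 and correlation r, the change score has variance 2(1−r)σ² and the ANCOVA residual has variance (1−r²)σ². The ratio is (1+r)/2. I take one further df for baseline and inflate the variance by 1 + 1/(N−4) for chance baseline imbalance. The noncentrality is then √[(n/2) ÷ ((1+r)/2 × (1+1/(N−4)))]. For example, with 18 per arm and r = 0.5, the variance factor is 0.75 × (1 + 1/32) = 0.773, the noncentrality is √(9/0.773) = 3.41, and with 33 df power is 85%.

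| Assumed r | 20 per arm | 19 per arm | 18 per arm |
|---|---|---|---|
| 0.3 | 93.2% | 91.8% | 90.0% |
| 0.5 | 89.2% | 87.3% | 85.0% |
| 0.7 | 84.8% | 82.5% | 79.9% |
| 0.9 | 80.2% | 77.7% | 75.0% |

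A simulation of 20,000 trials per setting agreed to within about 1 point (for example 0.852 at 18 per arm with r = 0.5). It contained no missing data, so these are complete-case powers, not powers for the repeated-measures model.

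**4. What the schedule allows.** Someone who misses session 5 may already have MOBID-2 scores from sessions 1 to 4. A change-score comparison or a session-5 ANCOVA discards these. A repeated-measures likelihood model uses them. fNIRS has no intermediate values, so no such recovery is possible for the second main test.

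**The case against.** The strongest reply is that this is a pilot of preliminary effects, with five daily sessions under live supervision, so few scores should be missing and the loss of power is small. Data collection is also reported complete for 20 participants at the first site (Protocol 12.0). If those are all who were randomised there and all have session-5 scores, further loss can come only from the other 20. The documents do not confirm either condition. The reply does limit the power point, but it does not supply a model or a missing-score rule.

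A reader might infer that the 80% power fails unless all 40 participants give a score. The documents do not support that. The normal formula also yields 20 per arm, and by that formula power is 81.1% with one score lost and 79.98% with two. Under baseline adjustment there may be no shortfall at all.

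A reader might also infer that the trial will in fact exclude participants without a session-5 score. The SAP does not say so, and the covariates in Protocol 10.0 suggest that some model is intended.

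In the other direction, the 24 against 20 local participants in Protocol 12.0 might be taken as a dropout allowance. The text attributes that gap to screen failures.

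Finally, the repeated-measures model is not the only way to close the gap. A named ANCOVA with a stated missing-data rule would also do so.

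**Conclusion.** The point holds in this form: the primary estimator and the handling of missing session-5 scores are unspecified, and the literal change-score reading is weaker than an analysis that the scheduled data already permit. It should be corrected, because the SAP commits to two formal tests in a trial of 40, where a few missing scores or a change of method could alter the result.

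The possible bias cannot be sized from the documents. The precision to be gained depends on an unknown correlation: complete-case power at 20 per arm rises from 79% unadjusted to between 80% and 93% for assumed correlations from 0.9 down to 0.3, with equal SDs and 1.0 in SDs of change. The stated power is essentially right for an unadjusted comparison at the planned size. It has little margin for loss, and that is secondary to the missing specification.

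**What to change.** Before arms are compared, amend the SAP as follows.

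- **Primary model.** A likelihood-based repeated-measures model of MOBID-2 at sessions 1 to 5, with baseline, arm, session, arm-by-session and baseline-by-session. Name the covariance structure, for example unstructured with a stated fallback if it does not converge, and use Kenward-Roger degrees of freedom. Include every randomised participant with any post-baseline score, and take the arm contrast at scheduled session 5. ANCOVA at session 5 is an acceptable simpler choice, but it does not use partial data.
- **Covariates.** Say whether the medication covariates of Protocol 10.0 enter the model.
- **Nonparametric analysis.** Keep it as a sensitivity analysis, not as a data-driven replacement for the primary.
- **Missing data.** Report by arm those with no post-baseline score, and add one sensitivity analysis for data not missing at random.
- **fNIRS.** Adjust for baseline among those scanned, report missing scans by arm, and acknowledge that this is a complete-case analysis.
- **Power wording.** State that the 80% is for an unadjusted comparison with 20 scored per arm. Do not carry the unadjusted figures over to the adjusted model. If its power is reported, give it over a stated range of correlations.

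The cost is SAP wording, modest extra analysis and a covariance choice in a 40-person trial. No new data are needed. Timing matters, because half of the planned participants are already reported as having completed data collection.

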## **10.0 Inclusion and Exclusion Criteria\***

A maximum of 40 persons with early-stage Alzheimer's disease and related dementias (ADRD) will be enrolled. Participants who are 50 to 90 years old will be considered eligible if they (1) have early- stage ADRD, (2) have caregiver-reported chronic pain (average pain in the past 3 months  $\geq$  3 out of 10), (3) have a caregiver willing to participate in the study who sees the participant at least 10 hours/week, (4) can speak and read English, and (5) have no plans to change medication regimens during the trial. The diagnosis of early-stage ADRD will be verified by PI based on Mini-Mental Status Exam score (generally 16-23), the blind/telephone version of the Montreal Cognitive Assessment (MoCA, generally 16-26), or Clinical Dementia Rating scores (generally 0.5-1.0). We will assess the use of medications that can influence responses to tDCS (e.g., selective serotonin reuptake inhibitors, beta-blockers) and include them as covariates in our statistical models. Participants will be excluded if they have any concurrent medical conditions that could confound the interpretation of outcome measures, pose a safety risk for any of the assessment or tDCS procedures, or preclude the successful completion of the protocol. Specific exclusion criteria are: (1) history of brain surgery, brain tumor, seizure, stroke, or intracranial metal implantation, (2) alcohol/substance abuse, (3) severely diminished cognitive function (i.e., Mini-Mental Status Exam score  $\leq$  15), and (4) hospitalization within the preceding year for neuropsychiatric illness. Participants who do not have a device with internet access will be provided a smartphone to use during the study.

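### The SAP names no primary test and lets an unthresholded visual check of the data choose between two unnamed methods; one baseline-adjusted model should be fixed in advance

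*SAP*

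**What the plan says.** The first paragraph of the SAP defines the primary comparison: "Our primary analysis will compare clinical pain changes from baseline to the final intervention session between the active tDCS and sham tDCS groups". It names no test or model. It plans two tests (MOBID-2 and fNIRS at Day 5), each at 0.025, and states that with 20 per group "we will be able to detect the expected effect size of 1.0 with 80% power at a significance level of 0.025".

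The second paragraph has all variables examined before any analysis, "using measures of central tendency and a visual inspection of histograms and quantile-quantile plots", followed by the rule "If the assumption of normality is not met, nonparametric approaches will be employed". It gives no numerical trigger. It does not say whether raw scores, changes or residuals are inspected, or whether the person judging them is blind to arm. It names no nonparametric method.

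Protocol section 10.0 says that use of medications that can influence the response to tDCS will be recorded, with SSRIs and beta-blockers as examples, and that the investigators will "include them as covariates in our statistical models". The SAP mentions no covariates.

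Protocol section 6.0, Table 1, schedules MOBID-2 at baseline and at every stimulation session, so the data for a baseline-adjusted analysis are already collected.

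**The concern.** MOBID-2 is a bounded 0 to 10 score (protocol section 6.0). With 40 values, its histogram and quantile-quantile plot will often be neither clearly normal nor clearly not, so the trigger becomes a matter of judgement. A comparison of means and a comparison of ranks answer different questions, so the judgement also settles what the primary result measures. Two competent analysts could follow the SAP to the letter and report different verdicts on the primary outcome.

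Two further gaps follow from naming no model. The power statement cannot be tied to the analysis that will actually be run. The covariates promised in the protocol also have no place in the analysis plan.

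**Working it through.** **Inputs.** From the SAP: 20 per group, effect size 1.0, 80% power, 0.025 per test (2 × 0.025 = 0.05 overall). Assumed because the documents do not say: two-sided testing, effect size in SD units, no dropout.

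**Step 1. Reproduce the 80%.** For a two-sample t-test the noncentrality is d√(n/2) = 1.0 × √10 = 3.162. With 38 degrees of freedom and two-sided 0.025 the critical value is 2.334, and the power is 0.793. The normal approximation gives 0.821 and a required 20 per group. Other readings do not fit: one-sided 0.025 gives 0.869 and two-sided 0.0125 gives 0.703 (both by t-test). The figure therefore describes a two-sided comparison of two means. A Wilcoxon rank-sum test on normal data has about 0.76.

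**Step 2. Type I error of the two-stage rule.** Simulation with 20 per arm at nominal 0.025, using Shapiro-Wilk p < 0.05 as a stand-in for the visual check. The shapes were normal, exponential, lognormal, t with 3 df, and integer 0 to 10 change scores.

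| How the test is chosen | Rejection under the null |
|---|---|
| Normality check on residuals | 0.024 to 0.027 |
| Normality check on pooled raw values | 0.022 to 0.025 |
| Either test kept after seeing both p-values | 0.028 to 0.031 |

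The worst case adds 0.031 − 0.025 = 0.006, or 0.6 points.

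**Step 3. How often the choice decides the verdict.** At a true effect of 1.0 SD, the share of trials in which exactly one test is significant is 2 × P(either) − P(t) − P(rank).

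| Data | t-test | Rank test | Either | Disagree |
|---|---|---|---|---|
| Normal | 0.791 | 0.757 | 0.804 | 2 × 0.804 − 0.791 − 0.757 = 0.06 |
| Exponential | 0.794 | 0.920 | 0.926 | 2 × 0.926 − 0.794 − 0.920 = 0.14 |

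In the exponential case about 13 of the 14 points are trials that only the rank test detects. For integer 0 to 10 change scores with an effect of 0.90 SD the powers are 0.699, 0.667 and 0.712 (either), so disagreement is 2 × 0.712 − 0.699 − 0.667 = 0.06.

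**Step 4. What a fixed baseline-adjusted model would deliver.** Let ρ be the baseline to Day 5 correlation, which the documents do not give. The SD of change is σ√(2(1 − ρ)) and the residual SD after baseline adjustment is σ√(1 − ρ²). An effect of 1 SD of change therefore becomes √(2/(1 + ρ)) residual SDs. Power uses 37 degrees of freedom and critical value 2.336.

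| ρ | Effect in residual SDs | × √10 | Power by formula | Power by simulation |
|---|---|---|---|---|
| 0.3 | 1.240 | 3.922 | 0.939 | 0.933 |
| 0.5 | 1.155 | 3.651 | 0.901 | 0.893 |
| 0.7 | 1.085 | 3.430 | 0.858 | 0.847 |

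The formula ignores chance baseline imbalance, so the simulated values (93%, 89%, 85%) are the ones to use. The t-test on change stays at 79%.

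If the effect of 1.0 instead means one SD at Day 5, the effects are 1/√(1 − ρ²) for the adjusted model and 1/√(2(1 − ρ)) for change. By formula the powers are 0.83, 0.90 and 0.98, against 0.63, 0.79 and 0.96. The adjusted model has more power on both readings.

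**Step 5. Cost of the medication covariates.** With three covariates (number assumed) that explain nothing, power against 1.0 SD falls from 0.793 to 0.790. If they explain 10% of the variance it is 0.834.

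**The case against.** The case for the SAP's rule is reasonable, and much of it stands.

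- **Error rate.** A reader might infer that the rule inflates the type I error to about 0.03. The documents do not support that. That figure needs an analyst who sees both p-values and keeps the better one, whereas the SAP places the check before any analysis. Under that order the error rate stays near 0.025. What remains is that blinding to arm is not stated.
- **Power of the fallback.** A reader might infer that the nonparametric route costs power. It does so slightly on normal data, where it should seldom be triggered (about 5% of trials under the stand-in check). On exponential data it gains: 0.92 against 0.79. The 14% disagreement there is largely a benefit of switching.
- **Covariates.** A reader might infer that the fallback discards the covariates promised in the protocol. The fallback is unnamed: a plain rank-sum test cannot carry covariates, but a rank-based analysis of covariance can. The SAP mentions none on the parametric route either, so the mismatch is between protocol section 10.0 and the whole SAP.
- **Baseline adjustment.** The gain in step 4 comes from adjusting for baseline, not from removing the fallback. It supports the proposed replacement and does not measure harm done by the current rule.
- **Pilot status.** The trial estimates preliminary effects, which lowers the stakes. It still plans formal tests at a corrected level, so the test should be identifiable in advance.

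**Conclusion.** The point holds as one of prespecification. The primary test is not named, and a subjective check with no threshold decides between two unnamed methods. Material inflation of the type I error is not shown: it is close to nil if the choice is made without sight of the results, and at most about 0.6 points per test otherwise. What is shown is that, at a 1.0 SD effect, the choice of test changes the verdict in about 6% (normal data) to 14% (skewed data) of trials. The 80% power claim fits a two-sided t-test and describes no other route. The SAP and protocol section 10.0 are unreconciled on covariates.

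These sizes rest on two-sided testing, a standardised effect size, no dropout, the simulated shapes, and the assumed correlations of 0.3 to 0.7. This should be corrected, but it does not invalidate the trial.

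**What to change.** Replace the normality sentence with one primary analysis: a linear model (ANCOVA) for MOBID-2 at session 5 with treatment arm, baseline MOBID-2 and a listed set of the medication covariates from protocol section 10.0. The list has to be written out, because the protocol gives only examples, and it should be short with 40 patients. State the two-sided 0.025 level and restate the power for this model.

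Report one named rank-based analysis as a sensitivity analysis only. Use residual plots to describe the fit, not to choose the test.

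A permutation p-value may be added. It is valid for the null of no treatment effect, provided the permutation follows the actual allocation scheme. The documents give only the 1:1 ratio, and protocol section 12.0 reports 20 subjects already completed at another institution, so the scheme would have to be written down first.

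The cost is a few sentences in the SAP and a few lines of SAS, with no extra patients or measurements. The change should be made before anyone sees outcomes by arm. The downside is real: if the data are strongly skewed, a fixed mean-based model can have less power than a rank test (unadjusted, about 0.79 against 0.92 for exponential data).
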